5.3.2 Planned recruitment rate

We have worked with sites to understand what is realistic, given current workforce pressures and research timelines. Therefore, the planned recruitment rate is 2 participants per week for up to 16 weeks.

5.3.3 Statistical Analysis Plan

5.3.3.1 Analysis of the reliability and validity of the PREMs

- We will conduct initial analyses in SPSS to check for normality, outliers, and missing values.
- Our goal is to assess the validity and reliability of the two PREMS. This will involve exploratory factor analysis, a reliability test (Cronbach's alpha coefficient), and a construct validity test.
- We will evaluate the reliability of the PREMs using the composite reliability values for each dimension.

My Medicines Journey: Assessing the feasibility and implementation of a Toolkit

- To assess reliability, we will test for internal consistency using Cronbach's alpha coefficient.
- To determine construct validity, we will examine convergent, discriminant, and predictive validity using a Student's t-test, correction and regression analysis, and an analysis of covariance.

5.3.3.2 Analysis of the Intervention Outcome Measures

We shall focus on descriptive statistics such as percentages, means and standard deviations to understand the key features of the data from the outcome measures (Healthcare utilisation, Medicine-Related Problems, Self-efficacy, QoL, and Adherence) and the staff survey.

Criteria to determine if the intervention should proceed to RCT will be refined in agreement with our project advisory board. We will apply 'Red', 'Amber', and 'Green' (RAG) criteria (Young et al., 2019), which we have previously applied in our work (ISCOMAT programme RP-PG-0514-20009). Key criteria will be based on recruitment, intervention delivery, and participant engagement:

Criteria	Green	Amber	Red
Rate of recruitment	2 participants per week per site	1 participant per week per site	0 participant per week per site
Loss to follow up at 2 months	<20%	21-35%	>35%
Intervention delivery >50% on fidelity rating scale	100%	50-99%	<50%
Participant engagement with intervention (use of checklist, self-management plan and engages with DMS)	>75%	40-74%	<40%
Evidence of feasibility to collect outcome measures	>75%	35-75%	<35%

We will regularly review progress against the RAG progression criteria at project meetings and assess whether these are achievable within a full trial. Where progress is 'amber', barriers to implementation should be resolvable and we will work with our project advisory group (PAG) to review and adapt methods within the feasibility study. If more than 50% of our RAG criteria result in 'red' scores, we will not progress to a further full trial.

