HRA Health Research Authority
ICF Informed Consent Form

ISRCTN International Standard Randomised Controlled Trials

Number

NHS R&D National Health Service Research & Development

NIHR National Institute for Health Research

NMS New Medicines Service
PI Principal Investigator
PCN Primary Care Network

PIS Participant Information Sheet

PPIEP Patient & Public Involvement, Engagement &

Participation

PREM Patient-Reported Experience Measure
PSRC Patient Safety Research Collaborative

QoL Quality of Life

RCT Randomised Control Trial
RfPB Research for Patient Benefit
REC Research Ethics Committee
WHO World Health Organisation

WP Work Package

My Medicines Journey: Assessing the feasibility and implementation of a Toolkit

iii. STUDY SUMMARY

Study Title	Assessing the feasibility and implementation of the 'My medicines journey' intervention: A multi-methods evaluation		
Internal ref. no. (or short title)	My Medicines Journey: Assessing the feasibility and implementation of a Toolkit.		
Clinical Phase			
Study Design	Feasibility study		
Study Participants	Older people living with frailty and one or more long-term conditions and who have had one or more changes to their medicines during admission.		
	Family carers		
	Hospital staff (pharmacy teams) and community pharmacists implementing the intervention.		
Planned Size of Sample (if applicable)	Phase 2: 168 older people (84 to receive intervention; 84 to act as 'control' to determine if it is feasible to collect outcome measures from a non-trial group)		
	20 Older people/informal carers for qualitative interviews		
	12 Hospital staff for qualitative interviews		
	Up to 8 Hospital Staff for the Focus group/feedback sessions.		
Treatment duration	2 weeks post-discharge		
Follow up duration	3 months post-discharge		
Planned Study Period	24 months		
	Objectives	Outcome Measures (feasibility)	
Primary	Validate a PREM Explore the acceptability of implementation of the PREM from the perspectives of patient participants and staff	 Rate of recruitment Loss of follow-up at 2 months Intervention delivery Participation engagement with the intervention Evidence of feasibility to collect outcome measures 	
Secondary	Consolidate RCT protocol and refine outcome measures.		
	Create a multi-site trial protocol		

My Medicines Journey: Assessing the feasibility and implementation of a Toolkit

V. FUNDING AND SUPPORT IN KIND

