My Medicines Journey: Assessing the feasibility and implementation of a Toolkit

viii. KEYWORDS: Older people

Medicines

Management

Intervention

Feasibility

Multi-methods

My Medicines Journey: Assessing the feasibility and implementation of a Toolkit

ix. STUDY FLOW CHART

Phase 1 (Completed)

- Development of a Patient Reported Experience Measure (PREM)
- Pilot and revise the questionnaire with 20 stakeholders
- This Phase has been completed

Phase 2

- Pre-test, post-test feasibility study
- Older people complete questionnaires at three-time points to measure patient experience (WP1 PREM) and healthcare utilisation
- Post-intervention semi-structured interviews to explore barriers and enablers to intervention use

Phase 3

 Consolidate implementation strategy and multi-site trial protocol My Medicines Journey: Assessing the feasibility and implementation of a Toolkit

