Materials to help older people manage their medicines (e.g., family carer packs and checklist)

Data collection: Questionnaires [(2 weeks (PREM 1, outcome measures x 5) and 3 months (PREM 2 & outcome measures x 5) post-discharge)]

Control arm delivery

Questionnaires at same time points as intervention arm (PREMs, EQ5D5L, baseline data, healthcare utilisation, adherence, self-efficacy, MRPs)

Assessment of feasibility

Documentary analysis/ routine data collection
Staff observation (various times over 8 weeks at each site)
Interviews with older people/carers (n=20)
Staff survey (n=30)
Staff Interviews (n=12)
Focus Group meetings (8 Hospital staff)

Synthesis and refinement

Findings
Refine outcome measures
Create a multi-site trial protocol

My Medicines Journey: Assessing the feasibility and implementation of a Toolkit

STUDY SETTING AND METHODS OF DATA COLLECTION AND DATA ANALYSIS

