5.2.1.1 Intervention arm delivery

This will involve the clinical team identifying suitable participants and research nurses consenting participants and administering a patient survey to collect baseline characteristics data. This phase will also include clinical teams providing older people with materials to help them manage their medicines (e.g., family carer packs and medicine management checklists). As part of our intervention implementation guide, we have developed a customised eight-step checklist to support delivery. Staff will be asked to complete this checklist, and we will use it, along with other data sources such as patient-reported and community pharmacy-reported information, to ascertain the level of fidelity. We will calculate the percentage of intervention each participant receives and use this to establish our progression criteria for future definitive trials (intervention delivery >50% on the fidelity rating scale). We will also use this information to further refine the intervention and implementation guide.

[figure not shown]
In addition, as part of the intervention arm delivery, the research team will administer questionnaires two (2) weeks after discharge to collect data on five (5) outcome measures (PREM1, EQ5D5L, healthcare utilisation, adherence, self-efficacy, and medicines-related problems (MRPs). Depending on the participants' preferences, these questionnaires will be administered either by post, telephone, or online (via a link provided to MS Forms).

Furthermore, the research team will administer a PREM 2 questionnaire (Appendix 9) and collect data on the five outcome measures from the same sample 3 months post-discharge. These questionnaires will be administered via post, telephone or online (Microsoft Teams or Zoom). Below is a flowchart illustrating the patient journey through the project/intervention.

As part of this feasibility study, we will explore what routine data can be collected, with the participants' consent, to aid with our analysis. Presently, we envisage that this will be routinely data about the participant's number of hospital readmissions and data from community pharmacy reporting systems about whether the Discharge Medicine Service was delivered to the participant.

My Medicines Journey: Assessing the feasibility and implementation of a Toolkit

My Medicines Journey: Assessing the feasibility and implementation of a Toolkit

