5.2.1.2 Control arm delivery

In addition to the intervention group, the clinical/ research team will recruit 84 older people to form the control group. This sample will be asked to complete patient surveys at the same time points, including PREMs, EQ5D5L, baseline data, healthcare utilisation, adherence, self-efficacy, and MRPs.

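### The loss-to-follow-up progression criterion is set at 2 months, but participants are followed up only at 2 weeks and 3 months, so it cannot be scored as written

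*Protocol*

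**What the plan says.** Two places set the criterion at 2 months. The RAG table in Protocol section 5.3.3.2 has "Loss to follow up at 2 months", with Green below 20%, Amber 21-35% and Red above 35%. The study summary (section iii) lists "Loss of follow-up at 2 months" among the feasibility outcomes. Neither says whether the 2 months run from discharge or from recruitment.

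The schedule is given in several places, and none has a 2-month contact:

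- The study flow chart (section ix): "Older people complete questionnaires at three-time points to measure patient experience".
- The workflow chart in section 4: "Questionnaires [(2 weeks (PREM 1, outcome measures x 5) and 3 months (PREM 2 & outcome measures x 5) post-discharge".
- Section 5.2.1.1, first follow-up: "the research team will administer questionnaires two (2) weeks after discharge to collect data on five (5) outcome measures".
- Section 5.2.1.1, second follow-up: the team will "collect data on the five outcome measures from the same sample 3 months post-discharge".
- Section 5.2.1.2, controls: "This sample will be asked to complete patient surveys at the same time points".
- The study summary gives a follow-up of 3 months after discharge.

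Section 3.3 makes meeting the progression criteria part of the primary outcome of this phase. Section 5.3.1, item A, sizes the assessment against those criteria on 84 intervention participants.

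**The concern.** A progression threshold should be tied to a moment at which the quantity is observed. Here the threshold sits between two questionnaires. A participant who goes quiet without formally withdrawing is recognised as lost only when a questionnaire falls due and does not come back, and none falls due at 2 months.

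To fill in the row, the team would have to use the 2-week return, the 3-month return or some interpolation. These can give different colours, and the protocol does not say which to use. If the choice is left until returns are in hand, the colour is no longer the result of a rule fixed in advance.

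**Working it through.** **1. Time points side by side.** Count from discharge and take 2 months as about day 61 and 3 months as about day 91.

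- Baseline: on the ward, before discharge.
- Questionnaire 1: day 14, which is 61 - 14 = 47 days before the criterion.
- Questionnaire 2: about day 91, which is 91 - 61 = 30 days after it.

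Baseline plus these two accounts for the three time points in the flow chart (my reading; the flow chart does not list them). If the 2 months ran from consent on the ward, day 61 would coincide with questionnaire 1 only for a patient discharged 61 - 14 = 47 days after consent. The choice of origin therefore does not remove the mismatch in general.

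**2. Other possible sources of a 2-month figure.**

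- The only eight-week activity is staff observation at the sites (section 5.2.1.3), which is not participant follow-up.
- Routine readmission and Discharge Medicines Service data (section 5.2.1.1) are exploratory and have no 2-month extraction point.
- Withdrawal may happen at any time (section 7.2) and can be dated. That captures active withdrawal only.

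**3. What could be recovered.** Dated withdrawals by day 61 give a lower bound on 2-month loss. All participants without a 3-month return give an upper bound, because anyone who returns that questionnaire was not lost at 2 months. With assumed counts of 5 early withdrawals and 21 missing 3-month returns among 84, the bounds are 5/84 = 6.0% and 21/84 = 25.0%. That range covers both Green and Amber.

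**4. Thresholds in participants (n = 84).** 0.20 x 84 = 16.8, so Green means 16 or fewer lost. 0.35 x 84 = 29.4, so Red means 30 or more lost.

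**5. Does the stand-in matter?** Two illustrations, both on assumed figures:

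- 15% lost at 2 weeks is Green; 25% lost at 3 months is Amber.
- Under a constant rate of loss from discharge, loss at 2 months = 1 - (1 - loss at 3 months)^(2/3). For 25% at 3 months this is 1 - 0.75^(2/3) = 17.5%: Amber at 3 months, Green at 2 months. In the other direction, 1 - 0.80^1.5 = 28% and 1 - 0.65^1.5 = 48%. So limits of 20% and 35% at 2 months would correspond to about 28% and 48% at 3 months.

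**6. Effect on the decision.** Section 5.3.3.2 rules out a full trial if more than half of the criteria are Red, which means at least three of five. A Green-to-Amber change cannot trigger that. This row changes the outcome only if the choice of time moves it into or out of Red while exactly two of the other four are Red.

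**The case against.** The strongest reply is that this is a wording slip in a descriptive feasibility study. Section 5.3.3.2 says the criteria will be refined with the advisory board, so the time could be settled before any 3-month data exist. A separate analysis plan might also address it. The first part stands to this extent: choosing the time after seeing returns is a risk, not a certainty. It does not remove the problem, because no date or rule for the refinement is given and progress is to be reviewed regularly as data accrue. Nor is this a detail left to an analysis plan. The protocol states a time that conflicts with its own schedule, and it does not show whether 2 weeks or 3 months was meant.

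It can also be said that the fifth RAG criterion, on whether outcome measures can be collected, already covers questionnaire return. It overlaps, but no time is stated for it, and it does not supply the figure for the loss row.

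A reader might infer more than the documents support:

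- *That the study learns nothing about 2-month status.* Too strong: withdrawals can be dated and bounds obtained, as shown above.
- *That the criterion belongs to no arm, so pooling could hide poor retention in controls.* Section 5.3.1, item A, ties the progression criteria to the 84 intervention participants, and item B gives the controls a separate purpose. No pooling is proposed.
- *That 3 months is the endpoint of the future trial.* The protocol does not fix that endpoint. The Background calls the PREM only a possible primary outcome, and PREM 1 is collected at 2 weeks.
- *That the mismatch endangers the go/no-go decision by itself.* The stop rule needs at least three Reds, and the illustrations here move only between Green and Amber.

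**Conclusion.** The mismatch is real and appears in two places. One of the five progression criteria has a time point 47 days after one scheduled contact and about 30 days before the next, so its percentage cannot be scored as written. Whichever questionnaire stands in for it can change the colour. The size of that effect rests on assumed loss rates, since the protocol gives none; the schedule conflict itself rests on no assumption beyond counting from discharge. The demonstrated consequence is a possible Green-to-Amber change, which affects whether methods are reviewed and adapted. An effect on stopping would need two other Red criteria as well. It should be corrected because the progression criteria are part of the primary outcome and the correction is nearly free.

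**What to change.** Before follow-up returns are reviewed:

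- Reconcile the time point in the study summary and the RAG table with a scheduled contact. Three months is the best supported choice, as it is both the stated follow-up duration and the final collection point.
- Define loss as no 3-month questionnaire returned, counting withdrawals as lost.
- Ask the advisory board to confirm that the 20% and 35% limits still apply at that time, since they are printed against an earlier one.
- Score the criterion in the 84 intervention participants. Report the 2-week return and control-arm retention alongside, as descriptive figures only.

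The cost is two wording edits, a one-line definition, a recorded confirmation from the board and a few extra figures in the report. No new data collection is needed. The drawbacks are that retention may look slightly less favourable than at an earlier time, and that the row will overlap somewhat with the criterion on collecting outcome measures.

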5.3 STATISTICS AND DATA ANALYSIS

5.3.1 Sample size calculation

We plan to recruit a diverse sample of 168 older people across 4 intervention sites and 4 control sites during hospital admission, plus hospital staff involved in delivering the intervention across the sites.

There are four varying sample size estimates for this study:

My Medicines Journey: Assessing the feasibility and implementation of a Toolkit

- A. To determine feasibility against the progression criteria (n=84 intervention participants) The sample size is based on the need to understand whether it is possible to consistently recruit 2 participants a week for up to 16 weeks per site and account for attrition. Based on previous feasibility studies, such as Teare et al. (2014) who determined that 70 measurable subjects are required when outcomes are continuous, we believe this is an appropriate sample size to determine feasibility against our progression criteria.
- B. To determine if data can be collected from a 'control' arm (n=84 control participants) Sample size is determined based on A, and contributes to C.
- C. To validate the PREM (n=168 patient participants)

 For validation studies, a widely used rule of thumb suggests 10 responses per item in the instrument.

The PREM contains 15 to 18 items, leading to a sample size in the range of 150 to 180.

The intended sample size is 168.

If this is achieved, the margin of error (for responses to each item) will be:

- A) +/- 7.5% assuming a proportion of 50% at the 95% confidence level
- B) +/- 5% assuming a proportion of 50% at the 80% confidence level

We consider this to be acceptable.

Extreme responses to the items (proportions higher or lower than 50%) will reduce the margin of error.

D. To collect in-depth qualitative data from a smaller sample of patient and staff participants (n=12-30 depending on methods)

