My Medicines Journey: Assessing the feasibility and implementation of a Toolkit Strongly Agree Not sure Disagree Strongly agree disagree I was able to stick to my medicine routine while in the hospital, and if I wasn't able to, the staff discussed it with me. Strongly Agree Not sure Disagree Strongly disagree agree These statements are about when you were preparing to leave the hospital 11. I was satisfied with the time it took to prepare my medicines to take home. Disagree Strongly Strongly Agree Not sure agree disagree I felt that my medicines needs were catered for when I was preparing to leave the hospital. Strongly Strongly Agree Not sure Disagree agree disagree

My Medicines Journey: Assessing the feasibility and implementation of a Toolkit

13. m	I was given o nedicines after		ation on who to spital.	contact for he	elp with my
	Strongly	Agree	Not sure	Disagree	Strongly disagree
	agree	\bigcirc	\bigcirc	\bigcirc	O
14. le	I felt prepare aving the hos		sponsibility for	my medicines	when I was
	Strongly agree	Agree	Not sure	Disagree	Strongly disagree
	Ö	\bigcirc	\bigcirc	\bigcirc	O
15.	I understood	any change	es to my medici	ines, including	:
	new medistopped n	cines, nedicines, aı	nd		
	changes i	n strength o	r dose.		
L	also knew wha	_			
	Strongly agree	Agree	Not sure	Disagree	Strongly disagree
	Ŏ	\bigcirc	\bigcirc	\bigcirc	Ŏ
16.	When I left the Strongly	ne hospital, l Agree	I had all the me Not sure	edicines I need Disagree	ded. Strongly
	agree				disagree
	\cup	\cup	\bigcup	\cup	\cup

My Medicines Journey: Assessing the feasibility and implementation of a Toolkit

I was told who was responsible for arranging supplies of medicines

after I returned	home.				
Strongly	Agree	Not sure	Disagree	Strongly disagree	
agree	\bigcirc	\bigcirc	\bigcirc	disagree	
•	-	knowledge, told out my changed		ty healthcare	
Strongly agree	Agree	Not sure	Disagree	Strongly disagree	
Ö	\bigcirc	\bigcirc	\bigcirc	disagree	
©Bradford Teaching Hospitals Trust					
Did you receive a	'My Medicin	es Journey' boo	oklet?	мунаме	
Yes	\bigcirc				
No	\bigcirc			MY MEDICINES	
Can't remember	\bigcirc			JOURNEY Helping you to: - Better understand the changes to your medicines while you're in troughtal - Get 0 to most out of your medicines when you get home.	
If 'yes' when did you use this?					
In hospital	\bigcirc				
At home	\bigcirc				
Not at all	\bigcirc				
Can't remember	\bigcirc				

If you received the booklet, how useful did you find it?

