My Medicines Journey	: Assessing the reasibility and implementation of a Toolkit
Very useful	
Quite useful	
Not useful	
•	'My Medicines Journey' booklet, did you contact any of eam for support or with questions about your which ones?
Please tick all tha	it apply:
GP	
Pharmacist	
Hospital	
Other (please write in)	
Section 2: Abou	t your medicines
medicines since y	ese next statements ask about any issues with your you got home from the hospital. Read each statement. always, sometimes, or never experienced that problem is.
1. I have prob	lems getting the medicines I need.
Never	Sometimes Always
\bigcirc	

My Medicines Journey: Assessing the feasibility and implementation of a Toolkit

I struggle to organ	nise my medicines at home	€.
Never	Sometimes	Always
\cup	\cup	\cup
3. I am not sure how to	store my medicines.	
Never	Sometimes	Always
4. I am not sure how to	get rid of unwanted medic	cines.
Never	Sometimes	Always
\bigcap		
	$igcup_{i}$	
5 Latruggla to physical	lly taka my modicinas (a a	ewallowing or injecting
them).	lly take my medicines (e.g.	swallowing of injecting
•	Comotimos	Alwaya
Never	Sometimes	Always
\bigcup	\bigcup	\bigcirc
6. I forget to take my	/ medicines.	
Never	Sometimes	Always
7. I have problems plar	nning when to take my med	dicines.
Never	Sometimes	Always
		\bigcap
		igcup

My Medicines Journey: Asse	ssing the feasibility and implement	ation of a Toolkit
Never	Sometimes	Always
\bigcirc		
9. I am not happy with	how my medicines affect m	ne.
Never	Sometimes	Always
10. I worry that taking effects.	g medicines for a long time	may cause future side
Never	Sometimes	Always
11. I do not know if n	ny medicines work well toge	ether.
Never	Sometimes	Always
\bigcirc	\bigcirc	\circ
12. Different healthca medicines.	are professionals tell me dif	ferent things about my
Never	Sometimes	Always
\bigcirc		\bigcirc
	nd the information I have be charge paperwork/packagir	•
Never	Sometimes	Always
		\bigcirc

	of using your medicines					
Ī	Your own way	Always	Often	Sometimes	Rarely	Never
	Instructions: Fo applies to you.	or each of t	he stateme	ents, please tid	ck the box v	which best
	Here are some w	vays peopl	e have sai	d they use the	ir medicine	S.
 We would like to ask you a few questions about how you use your medicines. 						
 This may differ from the instructions on the label or from what their doctor has said. 						
Many people find a way of using their medicines which suits them.						
,	Section 3: Abou	ıt taking y	our medic	cines		

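### The engagement progression criterion names three components, but no source described for all 84 intervention participants records patient use of the checklist or the self-management plan

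*Protocol*

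**What the plan says.** Section 5.3.3.2 lists five red/amber/green criteria. One is "Participant engagement with intervention (use of checklist, self-management plan and engages with DMS"), with green above 75%, amber 40-74% and red below 40%. The stopping rule reads "If more than 50% of our RAG criteria result in 'red' scores, we will not progress to a further full trial". Section 5.3.1 sets the sample for this purpose: "To determine feasibility against the progression criteria (n=84 intervention participants").

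The patient-reported items on the toolkit stand in Appendix 8 (Booklet 1, two weeks after discharge). They ask whether the My Medicines Journey booklet was received, then "If 'yes' when did you use this" (in hospital, at home, not at all, can't remember), then "If you received the booklet, how useful did you find it". A last item, containing "booklet, did you contact any of", offers GP, pharmacist, hospital or other. Appendix 9 (Booklet 2, three months) has no toolkit-use item. Section 4 of both booklets counts contacts with a community pharmacist.

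For DMS, Section 5.2.1.1 says that "we will explore what routine data can be collected" and expects this to include pharmacy system data on "whether the Discharge Medicine Service was delivered to the participant". The same section introduces an eight-step staff checklist, to be combined with patient and pharmacy reports to rate fidelity. Section 5.2.1.3 adds a review of intervention manuals for completion by staff, and interviews with up to 20 older people or carers.

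**The concern.** The criterion is about what patients did with three distinct parts of the intervention. Sections 1 and 4 also treat the patient-held checklist and the self-management or action plan as separate parts. The questionnaires that reach every participant do not distinguish these parts.

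The row would then have to be filled in one of two ways. Whole-booklet use would stand in for a three-part definition, although a patient who says the booklet was used may have used neither the checklist nor the plan. Alternatively, staff and pharmacy delivery records would stand in for patient behaviour. Section 5.2.1.1 already assigns those records to the fidelity row, so two of the five criteria would draw on the same evidence.

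This goes beyond detail that an analysis plan can settle. An analysis plan can state how to combine the components, but it cannot recover answers to questions that the booklets never asked.

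**Working it through.** **Step 1. Trace each component to every source described.**

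| Source (Protocol) | Reaches | Checklist used by patient | Plan used by patient | Engaged with DMS |
|---|---|---|---|---|
| Booklet 1, toolkit items (Appendix 8) | all who return it | not separable from the booklet | not separable from the booklet | asks whom the patient contacted; DMS not named |
| Booklets 1 and 2, service use (Appendices 8 and 9) | all who return them | no | no | counts community pharmacist contacts; DMS not named |
| Eight-step staff checklist (5.2.1.1) | intervention arm | stated purpose is fidelity | stated purpose is fidelity | stated purpose is fidelity |
| Manual review (5.2.1.3) | intervention arm | staff completion | staff completion | no |
| Pharmacy system data (5.2.1.1) | to be explored | no | no | delivery of the service |
| Interviews (5.2.1.3, Appendix 10) | at most 20 | yes, patient shows entries | yes, patient shows entries | asks whether the pharmacist made contact |

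Only the interviews look at patient use of the first two components. Coverage is at most 20/84 = 23.8% of the arm, and less if some interviewees are carers.

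The pharmacist-contact items do not isolate DMS for two reasons. Section 1 names a second post-discharge pharmacy service (NMS). The Booklet 1 item also asks whether the patient made contact, whereas the interview guide asks whether the pharmacist did. Delivery is not engagement either: Section 1 itself describes poor patient engagement as a difficulty for these services.

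**Step 2. Precision if only interviewees were scored.** The 95% half-width is 1.96 × √(p(1−p)/n) at p = 0.75.
- n = 20: 1.96 × √(0.1875/20) = 0.190, or ±19 points.
- n = 84: 1.96 × √(0.1875/84) = 0.093, or ±9 points.

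**Step 3. How much the combination rule matters.** The protocol gives no component rates, so let each component be used by a proportion q (assumption).
- All three: between max(0, 3q−2) and q; q³ if independent.
- At least one: between q and min(1, 3q); 1−(1−q)³ if independent.

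| q | All three: range | All three: independent | At least one: range | At least one: independent |
|---|---|---|---|---|
| 70% | 10-70% | 34% | 70-100% | 97% |
| 75% | 25-75% | 42% | 75-100% | 98% |
| 80% | 40-80% | 51% | 80-100% | 99% |
| 90% | 70-90% | 73% | 90-100% | 99.9% |

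At q = 75% under independence, the same behaviour scores amber by one rule (0.75³ = 0.42) and green by the other (1−0.25³ = 0.98). With other dependence, all three could fall to 25%, which is red. To exceed 75% on all three under independence, each component would need more than 0.75^(1/3) = 0.909, about 91%.

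**Step 4. Weight in the decision.** More than 50% of five criteria means more than 2.5, so at least three reds are needed to stop.

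**The case against.** A reader might infer that the criterion cannot be scored at all, or that it is a go/no-go item in its own right. The protocol supports neither reading. The questionnaire is not the only source: Section 5.2.1.1 envisages pharmacy data on DMS, both booklets count community pharmacist contacts, and staff records and interviews add more. Because stopping needs three reds, this row alone cannot stop progression. An amber result leads to review and adaptation.

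Other points carry some weight:
- Section 5.3.3.2 says that the criteria will be refined with the advisory board, and a combination rule could properly be left to an analysis plan. This stands for the rule but not for the missing data items.
- Section 4 has staff complete the action plan together with the patient, so a completed plan shows some patient participation. It shows nothing about use at home.
- The eight steps of the staff checklist may be in a figure that I could not see, so I claim nothing about their content. Their stated purpose is fidelity.
- The checklist and plan may be pages of the booklet. Whole-booklet use would then be related to component use, but would still not identify it.
- Parts of one toolkit are unlikely to be used independently, so 42% is one point in a range of 25-75%. The criterion's wording also favours requiring all three over any one.

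**Conclusion.** The concern holds in a limited form. No source described for all 84 intervention participants records patient use of the checklist or of the self-management plan. For DMS there is an exploratory, delivery-based source and contact items that do not name the service. With these sources the engagement percentage would rest on whole-booklet use or on delivery data already used for fidelity, and no rule for combining the components is given.

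The consequence is a band that depends on an unstated choice. At an assumed 75% use of each component, the row could lie anywhere from 25% to 75% under an all-three rule and from 75% to 100% under an any-one rule. These figures illustrate sensitivity and are not forecasts, because the protocol gives no component rates and no information on their dependence. The row is one of five and does not settle progression, but it would tell the designers of the full trial little about whether patients used the self-management parts. The gap is cheap to close before follow-up and cannot be closed fully afterwards.

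**What to change.** Add three short items (yes / no / can't remember) to Booklet 1 for intervention sites:
- used the checklist;
- used the self-management or action plan;
- whether the community pharmacist discussed the medicines with the patient after discharge, as follow-up to the hospital stay.

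Use pharmacy DMS records where they are obtained and the patient's answer otherwise. Name the source for each component in Section 5.3.3.2, and state that a participant counts as engaged when all three are met, in line with the criterion's wording.

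Report each component, and the all-three percentage among participants with data. Add a sensitivity figure that counts unknowns as not engaged. That figure should not be the main one, because it would mix attrition, which has its own row, into engagement. If non-responders had no other source, 20% non-response would cap engagement at 80%, and 0.75/0.80 = 94% of responders would have to meet all three to reach 75%. At 25% non-response the cap is 75% and green is impossible.

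The cost is about a minute per participant, a minor booklet amendment and a probably lower engagement percentage. The advisory board should therefore confirm the cut-offs against this definition before data are seen. It should also assign exactly 75%, which 63/84 gives and which falls in no band.
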